8.2 Subject Diary Data

A subject diary will be dispensed to all subjects for daily completion for 28 days beginning on injection day for each treatment with direct questioning for injection site responses: pain, tenderness, redness, bruising, swelling, itching and other. The presence and maximum intensity shall be assessed for the treated area:

Table 3. Grading for subject diary data

| Category |
|--------------------------|
| None |
| Tolerable |
| Affects daily activities |
| Disabling |

Number and percentage of subjects reporting each of the pre-defined, expected, posttreatment symptoms listed above, as collected in the 28 days diary, will be presented in total and by maximum intensity for each treatment session. Number of days with the event will be presented for each treatment session by category: 1, 2-7, 8-14, and 15-28 days. A bysubject listing will also be provided.

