## 7.2.1 Subject Diary Data

A subject diary will be dispensed to all subjects for daily completion for 28 days beginning on injection day for each treatment with direct questioning for injection site responses: pain, tenderness, redness, bruising, swelling, itching and other. The presence and maximum intensity (grading for subject diary in Table 3) shall be assessed for the treated area.

Injection site responses that have not been pre-defined in the diary may also be recorded in the diary under "other".

Diary data will be counted and displayed separately from other AE data. All pre-defined diary events ongoing at Day 28, shall be followed up until resolved.

Print date:

2021-08-25 16:18

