3.2 Study Endpoints

3.2.1 Safety Endpoints

- 1. Incidence, intensity, time to onset and duration of adverse events (AEs) collected throughout the study period.
- 2. Incidence, intensity, time to onset and number of days of pre-defined expected posttreatment events collected using subject diaries for 28 days from each treatment.
- 3. Pain assessment using a CCI in the immediately post treatment and 30 minutes post treatment.

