4.4 Sample Size

The sample size of approximately 30 subjects is not based on a statistical calculation. The selected number of subjects is regarded as enough for an evaluation of safety and effectiveness in this pilot study.

5 General Considerations

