8.1 Adverse Events

All adverse events (AEs) will be assigned to a PT and will be classified by Primary SOC according to MedDRA version 24.1 or later.

Any AE which started at or after the first administration of study treatment will be considered as Treatment Emergent Adverse Event (TEAE). If the start date is missing for an AE, the AE will be considered to be treatment emergent. Missing classifications concerning study treatment relationship will also be considered as treatment-related.

A summary of all AEs, will be provided, which will include:

- Number of subjects with at least one AE and number of events (in total as well as serious AEs)
- Number of subjects with at least one related AE and number of events (in total as well as serious AEs)
- Number of subjects with at least one unrelated AE and number of events (in total as well as serious AEs)
- Number of subjects who did not have an AE

The number of subjects with AEs related to study product or injection procedure as well as the number of events will be summarized by SOC, PT, and maximum intensity. In addition, for related AEs the number of days to onset and the duration of event will be summarized by SOC and PT. Action taken for related AEs will also be summarized. Serious AEs will be listed as well as related AEs with late onset (>21 days after most recent treatment).

Non-related AEs will be summarized by SOC, PT, and maximum intensity.

Events that occurred before the first administration of study treatment are included as Medical History.

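### The diary summary in SAP 8.2 does not separate symptoms that resolved within the diary from those still present when it closed at Day 28

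*SAP*

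**What the plan says.** Safety endpoint 2 (Protocol 3.1.3, SAP 3.2.1) covers incidence, intensity, time to onset and number of days of the expected post-treatment symptoms, "collected using subject diaries for 28 days from each treatment". Under SAP 8.2 the diary is issued "for daily completion for 28 days beginning on injection day for each treatment".

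The planned summary of days is: "Number of days with the event will be presented for each treatment session by category: 1, 2-7, 8-14, and 15-28 days". SAP 8.2 adds: "A bysubject listing will also be provided".

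Protocol 7.2.1 sets two further rules. On persistence: "All pre-defined diary events ongoing at Day 28, shall be followed up until resolved". On presentation: "Diary data will be counted and displayed separately from other AE data".

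For adverse events, SAP 8.1 plans that "for related AEs the number of days to onset and the duration of event will be summarized by SOC and PT", and SAP 5.6 reports how many AEs were ongoing when the study ended. For diary symptoms, the visible text of SAP 5.6 derives time to onset only. It gives no duration and no ongoing status. Protocol 7.2.5.3 allows diaries to be a source of AE information, but neither document says whether a diary symptom ongoing at Day 28 becomes an AE.

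**The concern.** The table is capped at the length of the diary, and the cap is not flagged. A subject whose swelling cleared and a subject whose swelling was still present on the last diary day can sit in the same row. A symptom that starts late and persists can sit in a row that reads as brief.

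Protocol 6.3.3 expects common injection reactions to clear typically within about a week. A symptom still present at Day 28 is therefore well outside expectation and is something a safety reader would look for. The protocol already asks sites to follow these symptoms, yet the SAP plans no summary that uses the result. Protocol 2.1 says the pilot's results are meant to support the decision on a pivotal study, so how often reactions outlast the diary is worth a line in the report.

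**Working it through.** **No plan figure to reproduce.** The plan attaches no number to this point, and on size it says: "The sample size of approximately 30 subjects is not based on a statistical calculation". The check applies the SAP 8.2 categories to example symptoms.

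**Inputs.** Diary Days 1 to 28, with Day 1 the injection day (SAP 8.2). Categories 1, 2-7, 8-14 and 15-28 (SAP 8.2). Assumption: the symptom is present every day from onset day s to end day e.

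**Formulas.** Diary days counted = min(e, 28) − s + 1. Elapsed duration = e − s + 1.

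| Onset s | End e | Elapsed days | Diary days counted | Row in table |
|---|---|---|---|---|
| 1 | 15 | 15 | 15 | 15-28 |
| 1 | 28 | 28 | 28 | 15-28 |
| 1 | 60 | 60 | 28 | 15-28 |
| 1 | 180 | 180 | 28 | 15-28 |
| 14 | 60 | 47 | 15 | 15-28 |
| 15 | 60 | 46 | 14 | 8-14 |
| 20 | 60 | 41 | 9 | 8-14 |
| 22 | 60 | 39 | 7 | 2-7 |
| 28 | 60 | 33 | 1 | 1 |

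**All onset days.** For any symptom continuing past Day 28, the count is 28 − s + 1 = 29 − s.

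- 29 − s is 15 or more when s is 1 to 14: 14 onset days, row 15-28.
- 29 − s is 8 to 14 when s is 15 to 21: 7 onset days, row 8-14.
- 29 − s is 2 to 7 when s is 22 to 27: 6 onset days, row 2-7.
- 29 − s is 1 when s is 28: 1 onset day, row 1.

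That gives 14 + 7 + 6 + 1 = 28. On 14 of the 28 possible onset days, a symptom that outlasts the diary lands below the top row. These are counts of onset days, not of events. Onset days are not equally likely, so half is not an estimate of how often misplacement would occur.

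**Would an ongoing row be empty?** The documents give no rate of symptoms outlasting the diary. If the per-subject rate were p, the chance of at least one such subject among 30 is 1 − (1 − p)^30. For assumed p of 2%, 5%, 10% and 20% this is 45%, 79%, 96% and 99.9%. A row for ongoing symptoms could well be populated even at a low rate, but that depends wholly on the assumed p.

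**The case against.** The strongest reply is that the table answers the endpoint exactly. Endpoint 2 is a 28-day diary measure, a 28-day diary cannot yield more than 28 days, and 15-28 is the correct top category. That stands. A reader might infer that the SAP breaches its own endpoint or leaves part of it unanalysed, and the documents do not support that reading.

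A second reply is that persistent reactions are not lost. SAP 8.2 plans a by-subject listing, which is readable case by case with about 30 subjects. Subjects are asked about AEs at every visit, and diaries may feed AE reporting. Related AEs get a duration summary in SAP 8.1 and, under Protocol 7.2.6, are followed after study end. This stands in part. It rules out the inference that persistent reactions are hidden from the report altogether. It does not close the gap in the summary, because the SAP does not say the listing will show status at Day 28 or a resolution date. Nor does either document say a diary symptom ongoing at Day 28 is entered as an AE.

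Third, a reader might assume the resolution date is already in the database. Protocol 7.2.1 requires the follow-up, but no visible text says where the date is recorded, and the eCRF and table shells are not among the documents. The shells may already contain an ongoing row.

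A reader might also infer that an unresolved symptom will be counted as new in the next session's diary. Sessions are 28 to 42 days apart (4 weeks, plus up to 2 weeks), so this is possible. But the diary is collected and reviewed at the next treatment visit, and the documents do not say how such a symptom would be recorded.

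**Conclusion.** The point holds as a limitation of the summary table, not as a fault in the endpoint. Followed as written, SAP 8.2 truncates symptom days at 28 without showing which symptoms were truncated. A symptom continuing past Day 28 is placed in 15-28 if it began on Days 1-14 and in a shorter row if it began later. The follow-up that Protocol 7.2.1 requires has no planned summary.

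The placement of rows assumes a symptom present every day. The table counts days on which a symptom was recorded, not elapsed time, so an intermittent symptom would be counted lower still. It would be too strong to say that every long reaction looks like one that ended on Day 15: that match needs a symptom present daily from Day 1, and late-onset persistent symptoms fall in lower rows instead. How many subjects would be affected cannot be stated from the documents. The importance is low: this is a reporting improvement in a descriptive pilot.

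**What to change.** In SAP 8.2, add for each pre-defined symptom and each treatment session the number and percentage of subjects with the symptom ongoing at Day 28. Derive it from the Day 28 (last) diary entry, and show subjects with no Day 28 entry as missing so that they are not read as resolved. The existing day categories can stay, since they match the endpoint.

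Where the eCRF captures the resolution date from the Protocol 7.2.1 follow-up, add it to the by-subject diary listing. Add one sentence stating whether diary symptoms ongoing at Day 28 are also recorded as AEs and so enter the duration summary in SAP 8.1.

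The cost is one table row per symptom and session and one sentence, with no new data for the Day 28 count. The listing column is equally cheap if the resolution date has a field in the eCRF. That should be checked first, together with the table shells.

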8.4 Pregnancies

For all women of childbearing potential, including those currently using contraception, a urine pregnancy test will be performed at screening, all treatment visits (prior to treatment) and at the final study visit at Month 12. The test result must be negative for the subject to receive any treatment with study product and will be documented in source data and the eCRF. Pregnancy test results will be listed only.

8.5 Device Deficiency

A device deficiency is defined as an inadequacy of a medical device with respect to its identity, quality, durability, reliability, safety, or performance. Device deficiencies will be listed only.

8.6 Device Palpability

Device palpability will be assessed at each scheduled visit post-treatment by a qualified staff member and will assess whether the palpability is the normal expected feel. An unexpected feel is to be recorded as an AE. Device palpability will be listed only.

9 Summary of Changes to the Protocol

None

10 Technical Details

All analyses in this SAP will be generated using SAS version 9.4 or higher, unless otherwise specified, and includes the following packages: Base SAS, SAS/STAT, SAS/GRAPH, SAS/Secure 168-bit, SAS/Secure Windows, SAS Enterprise Guide, SAS/ACCESS Interface to PC Files, SAS Workspace Server for Local Access, and High-Performance Suite.

11 References

^[1] US Federal Register. International Conference on Harmonisation; Guidance on Statistical Principles for Clinical Trials. Department of Health and Human Services: Food and Drug Administration [Docket No. 97D-0174]. Federal Register Volume 63, Number 179, pages 49583-49598. 16 September 1998.

https://www.ich.org/fileadmin/Public_Web_Site/ICH_Products/ Guidelines/Efficacy/E9/Step4/E9_Guideline.pdf

^[2] American Statistical Association. Ethical Guidelines for Statistical Practice. Prepared by the Committee on Professional Ethics, 07 August 1999. http://www.amstat.org/profession/ethicalstatistics.html

^[3] Royal Statistical Society. The Royal Statistical Society: Code of Conduct, August 1993. http://www.rss.org.uk/about/conduct.html

12 List of Planned CSR Tables, Listings, and Figures

Please reference document "43CASA2006 Statistical Analysis Plan TLF Shells v1.0" for the complete list of all tables, listings, and figures (TLFs) as well as corresponding mock shells. Minor changes made to the layout or formatting of the TLFs after SAP finalization will not necessitate a modification to the SAP.
